7.2 Important Protocol Deviations

Important protocol deviations are defined as protocol deviations that fall into the following categories:

- Violated key inclusion/exclusion criteria
 - Patient did not have advanced or metastatic RCC with a clear-cell component
 - Patient received prior systemic therapy
 - Patient had active brain metastases
 - Patient did not meet inclusion/exclusion criteria for lab values (e.g., absolute neutrophil count [ANC], platelet count, hemoglobin, serum creatinine, alanine aminotransferase [ALT], aspartate aminotransferase [AST], total bilirubin, urine protein creatinine ratio [UPCR])
 - Patient had a Karnofsky Performance Status of less than 70%
 - Patient required more than 2 anti-hypertensive medications for managing hypertension
 - Patient received prior palliative radiotherapy within 2 weeks prior to randomization
- Received wrong treatment or significant incorrect dose
 - Treated differently from the randomized assignment
 - Relative dose intensity >125% for study drug (programmatically derived). Received important prohibited medication during study participation
 - Any antineoplastic therapy (i.e., chemotherapy, hormonal therapy, immunotherapy, extensive non-palliative radiation therapy, or investigational agent)
- Missing critical primary/key secondary efficacy assessment
 - The baseline disease assessment is missing in BICR data (programmatically derived)

- Stratification error
- Issues that affect patient rights
 - Patient did not sign the informed consent for the study before randomization (programmatically derived)
 - Patient developed withdraw criteria during the study but were not withdrawn (manual review)
- Other issues that may significantly impact the completeness, accuracy, and/or reliability of key study data or that may significantly affect a patient's rights, safety, or well-being

Final determination of important protocol deviations will be reviewed by the study team (including Clinical Trial Lead (CTL), the Medical Monitor, and the statistician).

The number and percentage of patients in each important protocol deviations category and sub-category will be summarized by treatment arm for the ITT I/P-risk population and ITT all-risk population. All protocol deviations will be listed.

7.3 Study Population

7.3.1 Demographics and Other Baseline Disease Characteristics

The following baseline data will be summarized and listed by treatment arms for ITT I/P-risk population and ITT all-risk population:

- Age
- Age categorization I (< 65, ≥ 65 years)
- Age categorization II (<65, ≥ 65 and < 75, ≥ 75 years)
- Age categorization III (<65, ≥ 65 and < 75, ≥ 75 and <85, ≥ 85 years)
- Sex (male, female)
- Ethnicity
- Race (White, Black, Asian, Other)
- Height
- Weight
- Geographic region (US, Rest of the world)
- Karnofsky performance status (<80, ≥80)
- IMDC prognostic score as per IRT (0, 1-2, 3-6)
- IMDC prognostic score as per EDC (0, 1-2, 3-6)
- TKI choice as per IRT (Sunitinib, Cabozatinib)

- Prior nephrectomy (Yes, No)
- Prior radiotherapy (Yes, No)
- Baseline liver mets as per BICR (Yes, No)
- LDH level ($\leq 1.5 \times \text{ULN}$, $> 1.5 \times \text{ULN}$)
- Hemoglobin ($< \text{LLN}$, $\geq \text{LLN}$)
- Corrected Calcium ($\leq \text{ULN}$, $> \text{ULN}$)
- Absolute neutrophil count (ANC)
- Platelet ($\leq \text{ULN}$, $> \text{ULN}$)
- Alanine aminotransferase (ALT)
- Aspartate aminotransferase (AST)
- Alkaline phosphatase ($\leq \text{ULN}$, $> \text{ULN}$)
- PD-L1 status ($\geq 1\%$, $< 1\%$, indeterminate or non-evaluable)
- All lesions (Investigator and BICR Assessments at Baseline): sites of disease, number of disease sites per patient
- Target lesions (Investigator and BICR Assessments at Baseline): presence of target lesions, site of target lesions, sum of reference diameter of target lesions, number of disease sites per patient
- Hepatic impairment (No [total bilirubin $\leq \text{ULN}$ and AST $\leq \text{ULN}$], Yes [total bilirubin $> \text{ULN}$ or AST $> \text{ULN}$])
- Renal impairment (No [creatinine clearance $\geq 60 \text{ mL/min}$], Yes [creatinine clearance $< 60 \text{ mL/min}$])

7.3.2 Medical and Cancer History

Cancer history will be summarized and listed for the ITT I/P-risk population and the ITT all-risk population, and will include the time since initial RCC cancer diagnosis, time since metastatic/advanced RCC cancer diagnosis, history of brain metastases, histology and sarcomatoid component.

Medical history collected at screening will be mapped by the Medical Dictionary for Regulatory Activities (MedDRA) and will be summarized by system organ class (SOC) and preferred term for the ITT I/P-risk population and the ITT all-risk population. For summary tables, a patient will be counted only once per SOC and preferred term.

7.3.3 Prior Systemic Cancer/Oncology Therapies

An eligible patient should not receive any prior systemic cancer/oncology therapies for RCC. All patients who received prior systemic cancer/oncology therapies for RCC are considered to have important protocol violations.

All prior systemic cancer/oncology therapies will be listed, if applicable.

7.3.4 Surgical History and Prior Radiotherapy

The number and percent of patients who had prior cancer-related surgery will be summarized by type of surgery for each treatment arm using the ITT I/P-risk population and ITT all-risk population. Patients who have undergone prior nephrectomy will be summarized.

The number and percent of patients who had prior radiotherapy will be summarized by type of radiotherapy for each treatment arm using the ITT I/P-risk population and ITT all-risk population.

All prior radiotherapy and surgical procedures will be listed.

7.3.5 Concomitant Radiotherapy and Procedures

The number and percent of patients who had concomitant radiotherapy will be summarized by site and type of radiotherapy for each treatment arm using the ITT I/P-risk population and ITT all-risk population.

The number and percent of patients who had concomitant procedures will be summarized by each coded procedure preferred term for each treatment arm using the ITT I/P-risk population and ITT all-risk population.

All concomitant radiotherapy and procedures will be listed.

7.4 Treatments and Medications

7.4.1 Prior and Concomitant Medications

Prior and concomitant medications will be coded according to Anatomical, Therapeutic Chemical Level (ATCL) classification and preferred drug name using the World Health Organization Drug Dictionary Enhanced (WHO-DDE).

Concomitant medications are defined as medications taken on or after the date of first dose of study drug, including medications initiated prior to the date of first dose of study drug and continued during treatment, and medications initiated on or after the date of first dose of study drug and within 100 days after last dose of study drug or initiation of new anticancer therapy – 1 day, whichever is earlier.

Concomitant medications will be tabulated for the Safety I/P-risk population and the Safety all-risk population by WHO-DDE ATCL-2 classifications and preferred term. If the ATCL-2 classification is missing, the next non-missing higher level of classification will be used (Level 1). If a patient reports the same medication multiple times, then the frequency reported for that medication will be incremented by only one. As with the medication, if a patient reports multiple medications within the same ATCL-2 classification then the frequency for that ATCL-2 classification will be incremented by only one. Percentages will be calculated using the total number of patients in the Safety I/P-risk population and the Safety all-risk population.

Prior medications are defined as medications taken starting prior to the first dose of study drug. Prior medications will be summarized for the ITT I/P-risk population and ITT all-risk population using the same analytical procedures as concomitant medications. For the medications initiated prior to the date of first dose of study drug and continued during treatment, they are considered as both prior medications and concomitant medications.

Number of patients that received narrow-range CYP substrates as concomitant medication will also be summarized.

Prior and concomitant medications will be presented in a data listing.

7.4.2 Immune Modulating Medication

The list of anatomic class, therapeutic class and generic name used for the selection of immune-modulating medication (IMM) will be provided at the time of the database lock.

The percentage of patients who received immune-modulating concomitant medications for

- Management of drug-related select adverse events (any Grade, Grade 3-5) by select AE category/subcategory (see Section 8.2 for select AEs)
- Management of IMAEs (any grade, grade 3-5) by IMAE category (see Section 8.2.2 for IMAEs) will be reported by medication class and generic term.

For each category/subcategory of drug-related select AEs (any grade, grade 3-5) and IMAEs (any grade, grade 3-5), the following will be reported:

- Total duration of IMM use (excluding overlaps), duration of high dose of corticosteroid, initial dose of corticosteroid, and tapering duration (summary statistics)

7.4.3 Subsequent Anti-Cancer Therapy

Subsequent anti-cancer systemic therapy will be summarized based on the ITT I/P-risk population and the ITT all-risk population, and tabulated using the WHO-DDE and ATCL-2 classifications and preferred term. The number and percent of patients who took at least one subsequent anti-cancer therapy will be calculated and presented by treatment group, ATCL-2 classifications, and preferred term.

7.4.4 Study Drug Exposure

Overall exposure to each study drug will be summarized for the Safety I/P-risk population and the Safety all-risk population. Overall exposure to each study drug will be summarized in terms of exposure duration, number of infusions/doses, and relative dose intensity. The following summaries will also be performed:

- Time from randomization to first dose of study therapy (0 to 5 days, > 5 to 7, > 7 to 14, > 14 to 21, > 21 to 28, > 28)
- Relative dose intensity (%) using the following categories: < 50%; 50 - < 70%; 70 - < 90%; 90 - < 110%; \geq 110%
- For Arm A, the number of patients with at least one dose infusion interruption, the reason for interruption, and the number of infusion interruptions per patient
- For Arm A, the number of patients with at least one dose delay (either study drug) or dose reduction (for NKTR-214 only) and their reason(s)
- For Arm B, the number of patients with dose reduction and dose missed will be tabulated along with their reason(s)
- For NKTR-214, the time to first dose reduction and time to first dose infusion interruption will be summarized using descriptive statistics (mean, median, minimum, maximum)

All study exposure data will be presented in a data listing.

7.5 Efficacy Analysis

7.5.1 Efficacy Analysis of Primary Endpoints

The primary endpoints are ORR by BICR in the ITT I/P-risk population and the ITT all-risk population, and OS in the ITT I/P-risk population and the ITT all-risk population. The overall alpha for this study is 0.05, which is split with 0.001 to evaluate ORR in the ITT I/P-risk population and the ITT all-risk population, and 0.049 to evaluate OS in the ITT I/P-risk population and the ITT all-risk population. All alpha levels are two-sided. The test in the ITT all-risk population is gated by the one in ITT I/P-risk population for both ORR and OS. That is, ORR in the ITT all-risk population will not be tested unless ORR in the ITT I/P-risk population is statistically significant; and similarly, OS in the ITT all-risk population will not be tested unless OS in the ITT I/P-risk population is statistically significant.

In addition, a fallback approach will be used to reallocate alpha from ORR to OS. If ORR is significant in the ITT I/P-risk population and the ITT all-risk population, the alpha of 0.001 will be passed to OS. OS in the ITT I/P-risk population can then be tested at 0.05 (instead of 0.049) level. If it is significant, the alpha of 0.05 will be passed to OS in the ITT all-risk population.

7.5.1.1 Objective Response Rate

Objective response rate (ORR) is defined as the number of randomized patients who achieve a best overall response of confirmed complete response (CR) or confirmed partial response (PR) based on BICR assessments (using mRECIST 1.1 criteria) divided by the number of all randomized patients. Best Overall Response (BOR) is defined as the best response, as determined by the BICR, recorded between the date of randomization and the date of objectively documented progression per mRECIST 1.1 criteria or the date of subsequent anti-cancer therapy (including tumor-directed radiotherapy and tumor-directed surgery), whichever occurs first. For patients without documented progression or subsequent anti-cancer therapy, all available response designations will contribute to the BOR determination. Confirmation of response is required at least 4 weeks after the initial response. A Best Overall Response of SD requires a minimum of 56 days on study from randomization to the date of the first imaging assessment.

The primary analysis is based on the ORR I/P-risk Population and the ORR All-risk Population. The ORR will be compared between treatment arms using a Cochran-Mantel Haenszel (CMH) test stratified by the stratification factors for analysis (IMDC prognostic score and TKI choice) at a 0.001 alpha level. The ORR difference between the two treatment arms with its 95% and 99.9% confidence interval (CI) will be calculated using CMH methodology and adjusted by the same stratification factors. The ORR and its corresponding 95% exact CI will also be calculated by Clopper-Pearson method (Clopper and Pearson, 1934) for each arm. The number and percentage of patients in each category of BOR per BICR (complete response [CR], partial response [PR], stable disease [SD], progressive disease [PD], or not evaluable [NE]) will be presented, by treatment arm.

The ORR per investigator assessment will also be analyzed as a sensitivity analysis, following the same approach as above. The ORR concordance rate will be computed as the frequency with which the investigator's assessment and BICR's assessment agree on classification of a patient as responder versus non responder.

The ORR for patients who received sunitinib and the ORR for patients who received NKTR-214 and nivolumab will be summarized and compared using the CMH test stratified by the stratification factor IMDC prognostic score.

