2.4.7 Rationale for Stratification by IMDC Prognostic Score and TKI Choice

The IMDC prognostic score (Section 2.2.1) is known to have a profound effect on patient prognosis in terms of survival in advanced RCC, and the effectiveness of some treatment options in previously untreated advanced RCC is dependent on the different risk groups (Heng, 2013; Motzer, 2018b). It was also considered important to stratify patients based on TKI used in case there are differences in outcomes based on TKI choice.

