5.17 Treatment Assignment and Patient Number Assignment

Each patient will be assigned a unique patient number after signing the ICF. Patient numbers will be used on all patients' study information. Patient numbers will not be reassigned.

An Interactive Response Technology (IRT) will be employed to manage patient randomization. Randomization stratification factors are described in Section 5.1.

For all countries, Nektar will supply NKTR-214 and nivolumab from a central source. With Sponsor approval, and depending on local health authority guidelines and drug availability, nivolumab, sunitinib, and cabozantinib may be obtained through commercial supply, the site pharmacy, or through a central source. Sunitinib and cabozantinib must both be approved by the local Competent Authority and commercially available (local sourcing of these agents may be permitted on an ad hoc basis). Choice of TKI for an individual patient randomized to Arm B will depend on what drug products are available at each medical center and the Investigator's choice. Selection of a drug product should be based on what would have been offered to that patient, should the patient not be participating in this trial. Agents that are not routinely available in the pharmacy at each medical center will not be considered "available therapy." The Investigator must have prior clinical experience with the control arm for the treatment of a patient with renal cell carcinoma.

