5.0 OVERALL STUDY DESIGN AND PLAN

5.1 Study Design

This is a multicenter, randomized, open label, Phase 3 study that will evaluate the efficacy and safety of NKTR-214 combined with nivolumab compared with the Investigator's choice of a TKI, either sunitinib or cabozantinib, in patients with previously untreated advanced RCC.

The treatment period of the study is divided into multiple treatment cycles with associated evaluations and procedures. One cycle of treatment is defined as 6 weeks. Results of the assessments must be reviewed and documented before administering the scheduled dose of study drugs. In certain circumstances, patients with progressive disease (PD) per mRECIST 1.1 but with otherwise stable or improved performance and clinical status may continue to be treated in the event of a perceived benefit per Investigator.

This study is divided into a Screening period, a Treatment period, and a Long-Term Follow-Up period, which will continue until withdrawal of consent, death, lost to follow-up, or study termination by the Sponsor.

Approximately 600 patients (including at least 500 patients with IMDC intermediate- or poor-risk and approximately 100 patients with IMDC favorable risk) with previously untreated advanced RCC will be randomized in a 1:1 ratio to the two treatment arms below:

- Arm A: NKTR-214 0.006 mg/kg IV Q3W combined with nivolumab 360 mg IV Q3W
- Arm B: Investigator's choice of either one of the following treatments
 - Sunitinib 50 mg po once daily for 4 weeks followed by 2 weeks offOR
 - Cabozantinib 60 mg po once daily

Randomization will be stratified by:

- IMDC prognostic score (0 [favorable risk] versus 1-2 [intermediate risk] versus 3-6 [poor risk]); laboratory data used to calculate IMDC score are based on central laboratory results)
- TKI choice (sunitinib versus cabozantinib)

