6.5 Stratification and Pooling

For stratified analyses, the randomization stratification factors (IMDC prognostic score and TKI choice) entered into the IRT system at the time of randomization will be used, as follows:

- IMDC prognostic score as entered in IRT (0 [favorable risk] vs 1-2 [intermediate risk] vs 3-6 [poor risk])
- TKI choice as entered in IRT (sunitinib vs cabozantinib)

The IMDC prognostic score will also be derived based on data entered in EDC. When deriving IMDC prognostic score, the latest assessment prior to or on the date of randomization will be used (if not available, then the latest assessment before the date and time of first dose of study drug will be used); if the site used local laboratory data for randomization, the local laboratory data collected in EDC cancer history form will be used. Discrepancies between IMDC prognostic score derived vs IMDC prognostic score as entered in IRT system will be summarized.

If the discrepancy between the IMDC prognostic score (0 vs 1-2 vs 3-6) derived versus as entered in IRT is $\geq 10\%$, a sensitivity stratified analyses using strata based upon derived IMDC

prognostic score per EDC and TKI choice will be performed for the primary and key secondary endpoints.

To avoid unstable estimates, if any stratum (defined by the stratification factors for analysis) have fewer than 6 patients (1% of the estimated total number of patients) or there are no events, that stratum will be pooled with the smallest adjacent stratum for analyses. The smallest adjacent stratum is defined as the stratum with the fewest number of patients or events if the former is a tie, and the adjacent stratum is defined as the stratum with one of the two factors at the same level.

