A stratified Cox proportional hazards model with treatment as the single covariate will be used to estimate the hazard ratio and corresponding 95% CI. The stratification factors will be the same as those used in the analysis of ORR (IMDC prognostic score and TKI choice) as defined in Section 6.5. The Kaplan-Meier method will be used to further summarize OS, including Kaplan-Meier curves, and medians with corresponding 95% CIs. The OS rates at fixed timepoints (e.g. 12 months, 24 months, depending on minimum follow-up) will also be estimated along with their corresponding 95% CIs.

A sensitivity analysis for OS using an unstratified logrank test will also be performed. The hazard ratio associated with treatment will be presented along with the corresponding 95% CI.

The status of patients who are censored in the OS Kaplan-Meier (KM) analysis will be tabulated for each treatment group using the following categories:

- On-study (on-treatment, in follow-up)
- Off-study (lost to follow-up, withdraw consent, never treated)

The OS for patients who received sunitinib and the OS for patients who received NKTR-214 and nivolumab will be summarized and compared using the Kaplan-Meier method. The median and 95% CI will be presented for each treatment group, and the stratified logrank test will be performed. The stratification factor IMDC prognostic score will be used.

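### The sunitinib-specific ORR and OS comparisons set sunitinib-treated Arm B patients against every treated Arm A patient, although a randomised sunitinib-stratum contrast is available

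*SAP*

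**What the plan says.** After the primary ORR analysis, SAP 7.5.1.1 adds: "The ORR for patients who received sunitinib and the ORR for patients who received NKTR-214 and nivolumab will be summarized and compared". For the method, the section then specifies a comparison "using the CMH test stratified by the stratification factor IMDC prognostic score". SAP 7.5.1.2 adds the matching sentence for survival: "The OS for patients who received sunitinib and the OS for patients who received NKTR-214 and nivolumab will be summarized and compared". It gives Kaplan-Meier medians and a stratified logrank test, and on strata says: "The stratification factor IMDC prognostic score will be used". Neither section limits the NKTR-214 plus nivolumab side to patients whose declared TKI was sunitinib.

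TKI choice is one of the two randomisation strata (Protocol 5.1, SAP 5.1). SAP 6.5 takes it from the IRT as entered at randomisation, so it exists for Arm A patients as well as Arm B. Protocol 2.4.7 gives the reason for the stratum: "It was also considered important to stratify patients based on TKI used in case there are differences in outcomes based on TKI choice". Protocol 5.17 describes how the choice is made: "Choice of TKI for an individual patient randomized to Arm B will depend on what drug products are available at each medical center", together with the investigator's preference.

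The primary ORR and OS analyses compare the arms as randomised and stratify by both IMDC score and TKI choice. In SAP 7.5.5, TKI choice appears only in the list of subgroups that may be explored, with unstratified estimates.

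**The concern.** The comparison leaves randomisation in two ways.

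- **Mismatched strata.** The control side holds only patients for whom sunitinib was chosen. The experimental side also holds patients who would have been given cabozantinib. The choice follows centre availability and investigator judgement, so the two kinds of patient may differ in prognosis. Stratifying by IMDC score removes the part that runs through risk group. It does not remove centre, country or investigator selection, and neither region nor site is a randomisation stratum.
- **Grouping by treatment received.** Patients who were randomised but never dosed drop out of both sides. The trial is open label, so failure to start can differ by arm. SAP 7.5.1.1 itself defines ORR over all randomised patients, and the OS censoring table in 7.5.1.2 has a never-treated category.

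At stake is the reading of a contrast on both primary endpoints. Protocol 2.4.4 describes sunitinib as the comparator in most recent advanced RCC studies, so this result is likely to be set beside other trials. As written, a difference may partly reflect who was selected for sunitinib.

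**Working it through.** **The plan's own figures.** The sunitinib comparison has no stated size, alpha or power. The related design figures were reproduced to confirm the setting. With n per arm and pooled rate p̄, power for two proportions is Φ{[δ − z·√(2p̄(1−p̄)/n)] / √[(p₁(1−p₁)+p₂(1−p₂))/n]}, at two-sided alpha 0.001 (SAP 6.2.1).

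- 250 per arm, 27% vs 45%: 0.821 (stated 82%).
- 300 per arm, 32% vs 50%: 0.887 (stated 89%).

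These power figures hold, and the concern does not depend on them.

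**Bias in ORR with no treatment effect.** Let q be the share of patients whose recorded choice is cabozantinib. Let δ be the response-rate difference, cabozantinib stratum minus sunitinib stratum, among patients on the same treatment. Neither is in the documents; both are assumptions.

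Arm A rate = (1−q)·p + q·(p+δ) = p + qδ. The sunitinib control rate is p. The expected difference under the null is therefore **qδ** instead of 0.

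Inputs: p = 32% (all-risk control rate, SAP 6.2.1), 300 in Arm A, 300(1−q) sunitinib controls, nominal two-sided 0.05. No IMDC adjustment is made, so δ should be read as what remains within IMDC groups.

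Example, q = 0.5 and δ = +10 points: Arm A rate 37%, bias 5 points, SE = √(0.37·0.63/300 + 0.32·0.68/150) = 0.0472. Bias/SE = 1.06, and the rejection probability is 18.5%.

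| q | δ (points) | Bias (points) | Null rejection at 5% |
|---|---|---|---|
| 10% | ±5 | ±0.5 | 5.2% |
| 10% | ±10 | ±1.0 | 5.8% |
| 30% | ±5 | ±1.5 | 6.5% |
| 30% | ±10 | ±3.0 | 10.9–11.2% |
| 50% | ±5 | ±2.5 | 8.3–8.4% |
| 50% | ±10 | ±5.0 | 18.5–19.3% |
| 70% | ±5 | ±3.5 | 9.5–9.6% |
| 70% | ±10 | ±7.0 | 23.5–24.5% |

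**Bias in OS with no treatment effect.** To first order, if the cabozantinib-choice stratum has h times the death hazard of the sunitinib-choice stratum, the expected hazard ratio is 1 − q(1−h). With h = 0.8 (assumption), q = 10% gives 0.98 and q = 50% gives 0.90. With h = 1.25, the same shares give 1.025 and 1.125. The sign is not known.

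**Cost of restricting Arm A.** The SE ratio, restricted to unrestricted, is √{[2/(300(1−q))] / [1/(300(1−q)) + 1/300]} = √[2/(2−q)]. Power is for 32% vs 50% at two-sided 0.05.

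| q | SE ratio | Power, all of Arm A | Power, sunitinib stratum only |
|---|---|---|---|
| 10% | 1.03 | 0.993 | 0.990 |
| 30% | 1.08 | 0.984 | 0.966 |
| 50% | 1.15 | 0.958 | 0.891 |
| 70% | 1.24 | 0.864 | 0.693 |

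In the restricted comparison the bias term qδ is zero by design.

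**The case against.** The strongest reply is that this is a supplementary analysis. No alpha is assigned to it, it is not among the six hypotheses in the error-control proof (SAP 15.3), and the confirmatory tests compare randomised arms with TKI choice kept as a stratum. That is right, and it limits how much hangs on the point.

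Second, the documents tie cabozantinib to intermediate and poor risk, and stratifying by IMDC score deals with exactly that. Protocol 5.17 also requires both TKIs to be locally approved and commercially available, which argues against a purely regional split. Both statements are fair. They narrow the residual selection to centre availability and investigator choice, which the same section still allows. The documents do not show that this residual is prognostic, or that it is not.

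Third, the sizes are assumed, and the direction could run against Arm A as easily as for it. This stands. The reported ORR of 46% for cabozantinib against 18% for sunitinib (Protocol 2.4.2) is a drug effect and cannot inform δ.

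Fourth, the TKI-choice subgroup already gives the randomised contrast. It is optional and unstratified, so it does not replace an IMDC-stratified test that is firmly planned.

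Fifth, the loss of precision is not trivial if many patients have cabozantinib as their choice: about 15% on the standard error at a 50% share. This is correct, but that is also where the potential bias is largest.

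**Conclusion.** The concern holds. Read literally, both sections compare one TKI stratum of Arm B with both strata of Arm A, as treated, with TKI choice left out of the stratification. The bias vanishes only if no patient has cabozantinib as the recorded choice, or if outcomes on the same treatment do not differ by TKI choice within IMDC group. Under the assumed ranges it is 0.5 to 7 ORR points in either direction. For OS, the null hazard ratio moves to between 0.98 and 0.90 if the cabozantinib-choice stratum has 0.8 times the hazard, and above 1 if its prognosis is worse. These sizes are illustrations; the textual finding does not depend on them. The effect of grouping by treatment received was not quantified. The primary ORR and OS conclusions and the family-wise error rate are not affected. This is a cheap and worthwhile correction to a supportive analysis.

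**What to change.** Amend one sentence in each of SAP 7.5.1.1 and 7.5.1.2:

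- Include only patients whose TKI choice recorded in the IRT is sunitinib, in both arms.
- Analyse them by randomised arm, using the same ORR and ITT populations as the primary analyses, stratified by IMDC score.
- State that the comparison is supportive and carries no alpha.
- Report the same analysis for the cabozantinib stratum as planned output, not as an optional subgroup.

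No new data are needed. The cost is precision: Arm A patients from the cabozantinib stratum leave the sunitinib comparison. At a 30% share, Arm A falls from about 300 to 210 and the standard error rises by about 8%; at 50% it rises by about 15%.
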